Ethical approval will be obtained from the Ethics Committee of College of Dentistry/University of Baghdad prior to study commencement. The patients were first evaluated by the principal investigator ([name]) to see if they were eligible for the research. Those who meet the inclusion criteria will be asked to assigned a comprehensive consent form prior to the start of trial.

Subjects/Materials

Subjects

Patients seeking for orthodontic treatment and their treatment will be planned with metal fixed orthodontic appliance (0.22" for both arches).

Materials

A- Orthodontic materials:

1-Moisture insensitive primers: Transbond MIP (3M Unitek Dental Products, Monrovia, CA, USA) and Assure Plus universal bonding resin (Reliance, Itasca, IL, USA).

2-Orthodontic adhesive: CONTEC lc (Dentaurum GmbH & Co. KG, [name]).

3-Molar tubes: Stainless steel Classic Roth Tube with 0.022 slot (IOS International Orthodontics Services, [name]).

4- 37% phosphoric acid: N-Etch (Ivoclar Vivadent, Schaan, Liechtenstein).

5- Metal fixed orthodontic appliance with 0.022 slot and a universal sequence of orthodontic archwires used to finish leveling and alignment stage of orthodontic treatment. Orthodontic archwires used with brackets during orthodontic treatment.

B- Other materials:

oil- and fluoride-free coarse pumice powder, a rubber prophylactic cup, distilled water, bond brush, dental cotton pellets, articulating paper (ArtEXACT, Becht, Offenburg, Germany).

Instruments/equipment

Instruments

Cheek retractors, tube tweezers, bracket position gauge, dental mirror, probe and tweezers.

Equipment

Light curing unit: (Light emitting diode, Eight teeth curing pen; Changzhou city, Jiangsu, P.R.China) Specification of light curing unit: Light intensity: 1500 mW/cm², Output wavelength: 380–515 nm.

Sample Size

To have adequate power (80%) to show a statistically significant difference ($P < 0.05$) in proportions with at least one failed molar tube after 6 months, the RCT needed 33 patients in each group using a log rank test ignoring the matching. This assumes a difference of 35 percentage points (45% versus 80%, hazard ratio = 3.6). As an approximate allowance for the effect of matching, an estimated 33 patients in total were required using a stratified log rank test for analysis (**Littlewood et al., 2001; Wenger et al., 2008**).

Procedure/Intervention

1-Sample Selection:

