Thirty-three consecutive patients will be eligible for the study if they fulfill the following inclusion criteria:

1. Patients need metal fixed orthodontic appliance with 0.22";
2. Complete set of permanent dentition with fully erupted molar teeth on both arches;

3. Intact 1st molars and mainly their buccal surfaces are free from caries, fillings, or gingival hyperplasia;
4. No occlusal interferences that can affect the ideal position of molar tubes, especially in the lower arch.

2- Randomization:

The primers will be randomly allocated using a split-mouth, cross-quadrant design. In each patient, two diagonal quadrants (i.e. upper right and lower left, or vice versa) will be randomly assigned to each primer group. The split-mouth design has several advantages over a complete randomization design: it compares treatments within patients so that variation between patients is eliminated (e.g. effect of the chewing habits of the patient). Furthermore, in terms of patient recruitment, which is always difficult to accomplish in clinical trials, at most half of the patients are needed in a split-mouth design compared with the corresponding whole-mouth design (**Lesaffre et al., 2009**). A potential disadvantage of the split-mouth design is that the treatment applied to one side can have a carry-across effect on the contralateral side of the mouth. This problem is limited with randomization (**Thiyagarajah et al., 2006**).

In order to ensure an equal distribution of primers between the right and the left side of the dental arches, the mouth of each patient will be divided into quadrants and the contralateral bonding pattern will be randomly alternated from patient to patient using a random plan generator (Randomization.com). A CONSORT diagram showing the flow of patients through each stage of the trial is shown in Figure 1.

3-Blinding:

This study will be Double-blinded in which neither the patients nor the trial staff know which one of the primers a patient has received. This can be achieved by placing the two primers in two similar masked bottles and giving them numerical coding i.e. number one and number two coding for either type of primer (**Schulz and Grimes, 2002**).

[figure not shown]

Figure 1 CONSORT flow diagram showing progress of subjects through the trial.

4-Procedure:

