All patients will receive the same instructions and will be seen at 3-4-week intervals. They will be, however, requested to inform the operator immediately and attend as soon as possible once a bond failure was apparent. They will be instructed to brush with a manual toothbrush using a fluoride-containing toothpaste.

5-Data collection:

Each patient will be monitored for 6 months. If a bond failed, the following will be recorded:

- (1) Tooth number where failure occurred;
- (2) Type of primer used;
- (3) Date of bond failure.

Only the first failure of tubes will be taken into consideration. The teeth with recycled or newer tubes replaced will not be considered.

Timetable

Table 1

	Procedure	Time (months)
1	Material preparation and availability	Two months
2	Patient recruitment	Four months
3	Follow up	Six months
4	Results analysis and interpretation	Two months
5	Thesis writing	Four months
	Total	Eighteen months

The follow up period ends after six months from the start of recruitment of each patient. A clinical trial with similar situations concluded that half (49.8 per cent) of the total bond failures occurred during the first 2 months of treatment (**Mavropoulos et al., 2003**). The probability of bond failure is greater immediately after bonding and during the first 3 months of bracket life (**Campoy et al., 2010**).

Stopping Rules:

No stopping rules.

Budget and Funding:

- The study is self-funded.

Ethical Approval:

- The protocol will be submitted to ethics committee.

Data Management and Analysis

The data will be analyzed using SPSS software version 28.0.1 (IBM, Chicago, Illinois, USA). To find if there is significant difference, the number of bonding failures will be compared using the chi-square test, the tube survival rate will be estimated using the Kaplan–Meier analysis. The Tube survival distributions with respect to primer material, tooth location (upper/lower, right/left side), patient's gender and age will be then compared by means of a log-rank test. Further analysis to investigate the effects of covariates will be carried out using the frailty Cox regression model with response time to failure.

Further Considerations

Pilot study

- A pilot study will NOT be conducted

Dissemination

- Postgraduate Thesis.

References

- Buonocore, M.G. (1955). A simple method of increasing the adhesion of acrylic filling materials to enamel surfaces. *Journal of dental research*, 34, 849-853.

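### Gender and age do not vary within a mouth but are tested by an ordinary log-rank on individual tubes, so their p-values are too small if tubes in a mouth are correlated (minor)

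*Combined protocol and SAP*

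**What the plan says.** The Data Management and Analysis section takes the tube as the unit. Tube survival distributions by primer, tooth location and the patient's "gender and age will be then compared by means of a log-rank test". No stratification, clustering or robust variance is mentioned. The next sentence adds: "Further analysis to investigate the effects of covariates will be carried out using the frailty Cox regression model". It does not list the covariates, name the unit that carries the frailty, or say whether this model or the log-rank test decides.

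The cluster structure comes from the design. Under Sample Selection, eligibility requires "Intact 1st molars and mainly their buccal surfaces are free from caries, fillings, or gingival hyperplasia". Under Randomization, "In each patient, two diagonal quadrants (i.e. upper right and lower left, or vice versa) will be randomly assigned to each primer group". All four quadrants are therefore used. One first-molar tube per quadrant, or four per patient, is an inference; the plan does not state the count.

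The Randomization section also recommends the split-mouth design because "variation between patients is eliminated (e.g. effect of the chewing habits of the patient". The Sample Size section says that "an estimated 33 patients in total were required using a stratified log rank test for analysis", as an allowance for matching the two primers within a patient.

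**The concern.** The ordinary log-rank variance assumes independent units. For a factor that is constant within a patient, the tubes in a mouth always fall in the same group, so positive correlation between them adds to the true variance of the test statistic and the formula misses it. The plan itself gives reason to expect such correlation: it names between-patient variation such as chewing habits as a reason for its design, and it plans a frailty model.

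The stratified log-rank in the Sample Size section does not help here. Stratified by patient, it carries no information on a factor that takes one value in each stratum.

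Two things are at stake. A chance difference in tube survival between genders or age groups may be called significant more often than 5% of the time. The log-rank and frailty results may also disagree, with no rule for which one counts.

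**Working it through.** **Inputs.** From the documents: 33 patients, 6 months of follow-up, P < 0.05 (taken as two-sided), and 45% versus 80% with hazard ratio 3.6. By inference: four tubes per patient, so 33 × 4 = 132 tubes. Not in the documents, so assumed: the within-mouth correlation, the gender split and age grouping, and the failure rate per tube.

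**The plan's own figure.** Read as failure-free proportions, 45% and 80% give ln 0.45 / ln 0.80 = 3.58, which matches 3.6. Read as failure proportions they give ln 0.20 / ln 0.55 = 2.69, which does not. Freedman's formula gives (1.96 + 0.84)² × [(1 + 3.6)/(1 − 3.6)]² = 24.6 events. The mean failure proportion is (0.55 + 0.20)/2 = 0.375, so 24.6/0.375 = 65.5 patients, or 32.8 per group. The stated 33 per group is reproduced, and the failure-free reading is used below.

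**Formula.** With four tubes per patient and within-patient correlation rho, the variance is understated by a factor of about 1 + 3·rho. The actual type I error is about 2 × [1 − Φ(1.96/√(1 + 3·rho))]:

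| rho (assumed) | 0 | 0.05 | 0.10 | 0.20 | 0.30 |
|---|---|---|---|---|---|
| Variance factor | 1.00 | 1.15 | 1.30 | 1.60 | 1.90 |
| Type I error | 5.0% | 6.8% | 8.6% | 12.1% | 15.5% |

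**Failure rates per tube.** Two rates are assumed, 5% and 10%, the same for both primers. A third setting takes the primer effect from the Sample Size section. With two tubes per primer in a mouth, treated as independent, the rates are 1 − √0.80 = 10.6% and 1 − √0.45 = 32.9%.

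**Simulation.** 33 patients × 4 tubes, no true gender or age effect, gamma patient frailty, all tubes censored at 6 months, no drop-out, patients split 16:17. Type I error of the tube-level log-rank (20,000 runs per cell in the first two rows, 10,000 in the third):

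| Tubes failing by 6 months | Variance 0 | 0.5 | 1 | 2 |
|---|---|---|---|---|
| 5%, both primers | 5.0% | 5.9% | 6.6% | 7.8% |
| 10%, both primers | 4.5% | 6.4% | 7.5% | 10.6% |
| 10.6% and 32.9% by primer | 4.0% | 7.0% | 9.2% | 13.0% |

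The correlations of 6-month failure are 0, 0.02, 0.05 and 0.09 in the first row and 0, 0.05, 0.09 and 0.17 in the second. In the third row they are about −0.02, 0.06, 0.12 and 0.22, for which the formula gives about 4.2%, 7.1%, 9.3% and 12.8%. Smaller repeat runs of the third row (4,000 and 6,000 per cell) gave 4.1–4.2%, 6.6–7.0%, 9.4–10.4% and 13.5–14.0%.

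**Uneven groups.** With an 8:25 split the error is 3.6–5.7% with 5% of tubes failing and 4.9–10.4% with 10% failing. Under the primer effect, a 10:23 split at frailty variance 1 gave 9.2%.

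**Candidate remedies.**
- Log-rank on each patient's first tube failure: about 4–6% in all settings, at 16:17 and 8:25.
- Score test with patient-clustered robust variance: 4.3–5.0% at 16:17 (4.9–5.5% under the primer effect), but 4.9–8.9% at 8:25, worst with 5% failing.
- Gamma-frailty Cox likelihood-ratio test at 16:17 (2,000–3,000 runs): 6.6–8.3% with 5% failing and 4.7–6.9% with 10%.

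**The case against.** The strongest reply is that the plan already contains a clustered analysis. The frailty Cox model follows directly, and in a split-mouth trial the patient is the natural frailty unit. It would therefore be wrong to infer that the plan ignores clustering. What remains is that the model is labelled further analysis, its unit and covariates are unstated, and nothing says that it overrides the log-rank. It can also be somewhat liberal when failures are rare, so deferring to it is not a complete answer.

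A second reply is that the size is assumed. That stands. The direction is firm given positive correlation, but the amount is not known, and with rare failures and uneven groups there is almost nothing to correct.

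A third is that little depends on these tests. That also stands. They are secondary and non-randomised. The second objective, read literally, asks how the primers compare between genders and ages, which is a different contrast from these main effects and is outside this point.

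Two stronger readings are tempting. A reader might infer an error near 16% from the plan's own assumptions by giving every tube the average rate, 1 − √(1 − 0.375) = 20.9%; that simulation reaches 15.6% at frailty variance 2. But it drops the hazard ratio of 3.6. Every mouth holds tubes of both primers, and that spread within the mouth makes the pooled test more conservative for a patient-level factor, so 13% is the matching figure. A reader might also infer that the primer test is invalid for the same reason. It is not: primer varies within the mouth, so this mechanism does not reach it.

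**Conclusion.** The point holds, as a minor one. The gender and age log-rank tests in the Data Management and Analysis section use the wrong independent unit, and their type I error exceeds 5% if tubes in a mouth are positively correlated. With similar-sized groups, the excess is up to about 3 points with 5% of tubes failing, 6 points with 10% failing, and 8 points under the plan's primer effect, each at frailty variance 2. With no correlation there is no inflation.

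These figures rest on four tubes per patient, gamma frailty, no drop-out and the assumed splits. The 10.6% and 32.9% rates also treat a primer's two tubes in a mouth as independent. Positive correlation would imply higher rates and somewhat more inflation. At the ceiling, where the two always fail together (20% and 55% per tube), 4,000 runs per cell gave 3.5%, 7.9%, 12.1% and 15.4%; that is a bound and not an assumption of the plan.

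The primer null hypothesis and the sample size are not affected.

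**What to change.** Remove gender and age from the tube-level log-rank sentence and name, before analysis, one patient-level method that governs conclusions for these two factors. For example: *Gender and age groups will be compared by a log-rank test on the time to each patient's first tube failure, and this test governs the conclusions for these factors. The frailty Cox model, with the patient as the frailty unit, is a supporting covariate analysis. Kaplan–Meier curves of tubes by gender and age are descriptive.*

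A score test from a Cox model with patient-clustered robust variance is a reasonable alternative if the groups are of similar size. Choose one, not both.

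This needs one or two sentences and no new data, since "Date of bond failure" is already recorded for each failure. The first-failure endpoint would be new: the Sample Size section's comparison "in proportions with at least one failed molar tube after 6 months" is counted per primer group, not per patient across both primers.

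The cost is less favourable gender and age p-values and, with the first-failure test, some loss of power when failures are common. For a true hazard ratio of 3 and a 16:17 split, power for first-failure log-rank versus robust score test is 40% v 42% with 5% of tubes failing in the reference group and 62% v 71% with 10%, without correlation. At frailty variance 1 it is 28% v 28% and 37% v 44%. At 20.9% failing, simulated without a primer effect, the gap widens to 79% v 95% and 40% v 57%.

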These primers are commercially available nowadays as Transbond MIP (3M Unitek Dental Products, Monrovia, CA, USA) and Assure Plus universal bond (Reliance, Itasca, IL, USA). In the cloud, many in vitro studies supports the manufacturers' claim that these two novel orthodontic systems provides sufficient shear bond strength of orthodontic attachments bonded under moisture contaminated conditions (**Goswami et al., 2014; Kumar et al., 2018; Hadrous et al., 2019; Stefański et al., 2019**).

Although these in vitro measurements provide useful information about the bonding efficiency of different types of materials, they should be interpreted with caution because of inherent limitations and because they cannot take into account a number of factors that play an important role in the mouth (**Eliades and Brantley, 2000**). For your information, no previous clinical study was conducted to evaluate the efficacy of these primers on bond failure rate, therefore; this randomized clinical trial will be conducted to be more representative of the clinical reality.

Aim and Objectives

Aim

To evaluate the clinical effectiveness of moisture insensitive primers in bonding molar tubes under moisture contaminated conditions.

Objectives

- 1- To evaluate and compare the clinical bond failure and survival rate of molar tubes using two moisture insensitive primers under moisture contaminated condition.

2- To compare the effectiveness of these primers between different arches, sides, gender and age differences.

The null hypothesis is that “there is no significant differences in the bond failure rate of molar tubes using Transbond MIP and Assure Plus universal bond under moisture contamination during the function of archwires used during leveling and alignment stage of orthodontic treatment”.

Methodology

Study design

A single-operator, a split-mouth, cross-quadrant, randomized controlled trial (RCT), with 1:1 allocation ratio.

Settings

Orthodontic patients seeking for orthodontic treatment with fixed orthodontic appliance will be recruited for this study. The study will be conducted in the Orthodontic Clinic at the College of Dentistry/University of Baghdad in addition to private dental clinics and Bab Al-Muadham specialized dental center in Baghdad, Iraq. Clinicians will be either specialist orthodontists or under training to become specialist orthodontists.

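### Age is assigned to a log-rank test with no age groups defined, and the form of age in the planned frailty Cox model is not stated

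*Combined protocol and SAP*

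**What the plan says.** Objective 2 (Aim and Objectives) is "To compare the effectiveness of these primers between different arches, sides, gender and age differences". The Data Management and Analysis section carries this out by listing primer, tooth location, gender and age as factors for comparing tube survival: "gender and age will be then compared by means of a log-rank test". It then adds: "Further analysis to investigate the effects of covariates will be carried out using the frailty Cox regression model with response time to failure".

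Primer, arch, side and gender come as ready-made groups. Age does not. No section gives age bands, a cut-point or a rule for choosing one, and the inclusion criteria under Sample Selection set no age limits from which a natural cut would follow. The frailty Cox sentence does not list its covariates or say whether age enters in years or in bands.

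The Sample Size section concerns the primer comparison only ("45% versus 80%, hazard ratio = 3.6"; "the RCT needed 33 patients in each group using a log rank test ignoring the matching"; then 33 patients in total after allowing for matching). It gives no figure for age.

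**The concern.** The one test that the plan names for age cannot be run until someone decides how to divide 33 patients by age, and the plan leaves that decision open. Two things are at stake. First, any grouping treats patients within a band as having the same age, so a gradual age effect is harder to detect than with age in years. Second, if the bands were settled after failures had been seen, more than one division could be tried and the most favourable reported, and the nominal 5% level would no longer hold.

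A further gap concerns what is tested. A log-rank comparison of age groups asks whether tubes fail sooner at some ages. It does not ask whether the difference between primers changes with age, which is the natural reading of Objective 2.

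**Working it through.** **1. The plan's own figure.** Inputs from Sample Size: 45% and 80%, hazard ratio 3.6, power 80%, significance level 0.05 (taken as two-sided). Reading 45% and 80% as failure-free proportions, HR = ln(0.45)/ln(0.80) = 3.58. Freedman's formula gives events = (1.960 + 0.842)² × [(3.58 + 1)/(3.58 − 1)]² ≈ 24.7. The mean event probability is (0.55 + 0.20)/2 = 0.375, so 24.7/0.375 ≈ 66 in total, or 33 per group. The stated 33 reproduces. Age plays no part in it.

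**2. Information kept by grouping.** For a linear effect, the share kept is the squared correlation between age and its grouped version. For a median split of a normal variable this is 2/π = 0.637, a loss of 36%. The documents give no age distribution, so the range is shown:

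| Assumed age distribution | Lost, median split | Lost, tertiles | Lost, quartiles |
|---|---|---|---|
| Normal | 36% | 21% | 14% |
| Uniform | 25% | 11% | 6% |
| Right-skewed (log-normal, exponential) | 41-52% | 25-35% | 18-26% |

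**3. What the loss means for power.** Assumptions: 33 patients, one time to first failure each, exponential times censored at 6 months, normal age, and 1 − 0.45 × 0.80 = 64% of patients failing. The 64% treats the two primers' failures as independent within a mouth. The age effects are illustrative, since the documents give none. Simulated power:

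- HR 1.65 per SD of age: 39-40% for a median split, 58-59% for continuous age.
- HR 1.82 per SD of age: 51-53% against 73%.

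A hand check at HR 1.65: expected events are 33 × 0.64 = 21.1. For continuous age z = √21.1 × ln 1.65 = 2.30, and Φ(2.30 − 1.96) ≈ 63%. For the median split z = 2.30 × √0.637 = 1.84, and Φ(1.84 − 1.96) ≈ 45%. The approximation runs a little high, but the gap is about the same.

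**4. False-positive rate with no true age effect.** As a rough guide, k independent tests at 5% give 1 − 0.95^k: 9.8% for two, 14.3% for three, 22.6% for five. Different cuts of the same patients overlap, so the rates were simulated, taking the smallest p-value over the cuts tried. Ranges cover 33 patients with one record each (30% to 64% failing), 33 patients with four independent tubes each (15% or 30% failing), and 66 or 132 independent records:

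| Cuts tried | False-positive rate, independent observations |
|---|---|
| One, pre-set at the median | about 5-6% |
| Two | 9-10% |
| Three | 12-15% |
| Five, between the quartiles | 16-19% |
| Nine deciles | 24-26% |
| All, from about the 10th to the 90th percentile | 32-42% |

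**5. Tubes as the unit.** The plan compares survival of tubes, about 33 × 4 = 132 of them, and all four in a mouth share one age. With 15% of tubes failing and an assumed gamma frailty variance of 0.5 to 1, an ordinary tube-level log-rank test gives 8-10% false positives even at one pre-set median cut. This comes from clustering rather than from the choice of cut, but it also favours assessing age in the frailty model.

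**The case against.** The best reply is that the next sentence of the plan already supplies the better method. A frailty Cox model for covariate effects is planned, age is an obvious covariate, and it can enter in years. This stands to the extent that the plan as a whole does not necessarily discard age information. It does not close the gap, because the model's covariates and the form of age are unstated and the log-rank test is still the only analysis named for age.

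A second reply also stands. Nothing in the documents says that cut-points will be tried, or that groups will be chosen after failures are known. A reader might infer that the trial must either miss a real age effect or manufacture a false one, with an error rate anywhere up to about 40%. The documents do not support that. One pre-set cut holds the error rate near 5% with independent observations, three or four pre-set bands lose well under a third of the information if age is normal, and reduced power is not the same as a missed effect. The highest rates need an exhaustive search that no one has proposed.

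It is also fair to say that the percentages rest on an assumed age distribution, assumed failure rates and assumed effect sizes, and that age is a non-randomised factor in the second-listed objective.

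**Conclusion.** There is a real gap in specification, with a modest consequence. The plan names for age a test that needs groups, defines none, and does not say how age enters the model that could do without them. Against a linear age term, grouping loses roughly 14% to 36% of the information for normally distributed age with two to four equal groups, and 6% to 52% across the distributions considered. The rise in false positives (12-15% for three cuts, 16-19% for five) is conditional on cuts being tried. It is a risk that pre-specification would remove, not a feature of the plan.

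A reader might go further and conclude that the trial's main result is affected. It is not: the primer comparison, its null hypothesis and the 33 patients do not depend on how age is handled. The change is worth making because it is cheap and uses a model the trial already intends to fit.

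**What to change.** In Data Management and Analysis:

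- Remove age from the factors compared by log-rank test.
- State that age in years enters the planned frailty Cox model as a continuous covariate, with the patient as the frailty unit, and that its hazard ratio (per year or per 5 years) will be reported with a 95% confidence interval.
- If Objective 2 is meant to ask whether the primer effect varies with age, add a primer-by-age term. An age main effect alone does not answer that question. The trial was not sized for this term, so it should be reported as an estimate with its interval.
- If Kaplan-Meier curves by age are wanted for display, fix one cut now and attach no p-value to it.

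The cost is a sentence or two, with no new data and no extra patients. The one downside is that a linear term can miss a non-linear age effect; a quadratic term can be added as a check.
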